## 6.4 Safety Variables

#### 6.4.1 Adverse Events

AE reporting will begin at Screening (Visit 1) and will continue until the end of the study (28 days from last dose of IMP, Visit 9 – Safety Follow-up). AEs will be reported by the subject (or, when appropriate, by a caregiver, support person, or the subject's legally authorized representative).

The investigator and any designees are responsible for detecting, documenting, and recording events that meet the definition of an AE or SAE and remain responsible for following up AE (see Section 6.4.1.5).

## 6.4.1.1 Definitions

An AE is any untoward medical occurrence in a study subject which does not necessarily have a causal relationship with this treatment. An AE can therefore be any unfavorable and unintended sign (including a clinically significant abnormal laboratory finding), symptom, or disease (new or exacerbated), temporally associated with the use of the IMP, whether or not considered related to the IMP.

Events meeting the definition of AE include:

- Any abnormal laboratory test results (hematology, clinical chemistry, or urinalysis) or
  other safety assessments (e.g., ECGs, vital signs measurements), including those that
  worsen from baseline, considered clinically significant in the medical and scientific
  judgment of the investigator (i.e., not related to progression of underlying disease)
- Exacerbation of a chronic or intermittent pre-existing condition including either an increase in frequency and/or intensity of the condition
- Signs, symptoms, or the clinical sequelae of a suspected drug-drug interaction
- Signs, symptoms, or the clinical sequelae of a suspected overdose of either study treatment or a concomitant medication. Overdose per se will not be reported as an AE/SAE unless it is an intentional overdose taken with possible suicidal/self-harming intent. Such overdoses should be reported regardless of sequelae.

Events not meeting the definition of AE include:

- Any clinically significant abnormal laboratory findings or other abnormal safety assessments that are associated with the underlying disease, unless judged by the investigator to be more severe than expected for the subject's condition
- The disease/disorder being studied or expected progression, signs, or symptoms (clearly defined) of the disease/disorder being studied, unless more severe than expected for the subject's condition
- Medical or surgical procedure (eg, endoscopy, appendectomy): the condition that leads to the procedure is the AE
- Situations in which an untoward medical occurrence did not occur (social and/or convenience admission to a hospital)
- Anticipated day-to-day fluctuations of pre-existing disease(s) or condition(s) present or detected at the start of the study that do not worsen (note: pre-existing conditions will be recorded as part of the subject's medical history).

## 6.4.1.2 Recording of Adverse Events

AEs should be collected and recorded for each subject from signing informed consent until the end of their participation in the study, i.e., from Screening until the subject has discontinued or completed the study, including the post-treatment Safety Follow-up period at the timepoints specified in the Schedule of Assessments (Table 1). AEs identified after signing the ICF and before dosing will be recorded as pre-treatment AEs. If AEs occur, the first concern will be the safety of the study subjects.

AEs may be volunteered spontaneously by the study subject, or discovered by the study staff during physical examinations or by asking an open, non-leading question such as 'How have you been feeling since you were last asked?' All AEs and any required remedial action will be recorded. The nature of AE, date (and time, if known) of AE onset, date (and time, if known) of AE outcome to date, severity, and action taken of the AE will be recorded together with the investigator's assessment of the seriousness of the AE and causal relationship to IMP and/or study procedure on an AE electronic case report form (eCRF).

When an AE/SAE occurs, it is the responsibility of the investigator to review all documentation (e.g., hospital progress notes, laboratory reports, and diagnostics reports) related to the event. It is **not** acceptable for the investigator to send photocopies of the subject's medical records to the sponsor in lieu of completion of the AE/SAE eCRF page.

There may be instances when copies of medical records for certain cases are requested by the Sponsor and/or CRO. In this case, all participant identifiers, with the exception of the participant number, will be redacted on the copies of the medical records before submission.

All AEs should be recorded individually in the study subject's own words (verbatim) unless, in the opinion of the investigator, the AEs constitute components of a recognized condition, disease or syndrome. In the latter case, the condition, disease or syndrome should be named rather than each individual symptom.

#### 6.4.1.3 Assessment of Adverse Events

Each AE will be assessed by the investigator with regard to the categories discussed in the sections below.

#### **Intensity**

The investigator will assess all AEs for severity in accordance with the following standard ratings:

- Mild: Ordinarily transient symptoms, does not influence performance of subject's daily activities. Treatment is not ordinarily indicated or may be minimal.
- Moderate: Marked symptoms, sufficient to make the subject uncomfortable. Moderate influence on performance of subject's daily activities. Treatment may be necessary to alleviate symptoms.
- Severe: Symptoms cause considerable discomfort. Substantial influence on subject's daily activities, or significantly affects clinical status. The subject may be unable to continue in the study and intensive treatment may be necessary.

When changes in the intensity of an AE occur more frequently than once a day, the maximum intensity recorded for the event should be noted.

Note: an event is defined as *serious* when it meets at least 1 of the predefined outcomes as described in the definition of an SAE (see later), NOT when it is rated as severe.

#### Causality

The investigator will assess the causality/relationship between the AE and IMP/study procedure. One of the categories described in Table 3 should be selected based on medical judgment, considering the definitions below and all contributing factors. In this study AEs will be considered related to IMP/study procedure if causality is ascribed as either related, probably related, or possibly related.

For each AE/SAE, the investigator must document in the medical notes that he/she has reviewed the AE/SAE and has provided an assessment of causality.

There may be situations in which an SAE has occurred and the investigator has minimal information to include in the initial report to the Sponsor. However, it is very important that the investigator always make an assessment of causality for every event before the initial transmission of the SAE data to the Sponsor.

The investigator may change his/her opinion of causality in light of follow-up information and send an SAE follow-up report with the updated causality assessment.

The causality assessment is one of the criteria used when determining regulatory reporting requirements.

Table 3 Assessment of Relationship of Adverse Events to IMP/Study Procedure

Related	A clinical event, including laboratory test abnormality, which occurs in a plausible time relationship to treatment administration, and which concurrent disease or other drugs or chemicals cannot explain. The response to withdrawal of the treatment (dechallenge*) should be clinically plausible. The event must be definitive pharmacologically or phenomenologically, using a satisfactory
Probably related	rechallenge † procedure if necessary.  A clinical event, including laboratory test abnormality, with a reasonable time sequence to administration of the treatment, unlikely to be attributed to concurrent disease or other drugs or chemicals, and which follows a clinically reasonable response on withdrawal (dechallenge). Rechallenge information is not required to fulfill this definition.
Possibly related	A clinical event, including laboratory test abnormality, with a reasonable time sequence to administration of the treatment, but which could also be explained by concurrent disease or other drugs or chemicals. Information on treatment withdrawal may be lacking or unclear.
Unlikely to be related	A clinical event, including laboratory test abnormality, with a temporal relationship to treatment administration which makes a causal relationship improbable, and in which other drugs, chemicals or underlying disease provide plausible explanations.
Unrelated	A clinical event, including laboratory test abnormality, with little or no temporal relationship with treatment administration. May have negative dechallenge and rechallenge information. Typically explained by extraneous factors (e.g., concomitant disease, environmental factors or other drugs or chemicals).

\*Dechallenge is when a drug suspected of causing an AE is discontinued. If the symptoms of the AE disappear partially or completely, within a reasonable time from drug discontinuation, this is termed a positive dechallenge. If the symptoms continue despite withdrawal of the drug, this is termed a negative dechallenge. Note that there are exceptions when an AE does not disappear upon discontinuation of the drug, yet drug-relatedness clearly exists (for example, as in bone marrow suppression, fixed drug eruptions, or tardive dyskinesia).

†Rechallenge is when a drug suspected of causing an AE in a specific subject in the past is re-administered to that subject. If the AE recurs upon exposure, this is termed a positive rechallenge. If the AE does not recur, this is termed a negative rechallenge.

#### **Seriousness**

An SAE is defined as any untoward medical occurrence that at any dose:

- Results in death.
- Is life-threatening; this means that the subject was at risk of death at the time of the event; it does not mean that the event hypothetically might have caused death if it were more severe.
- Requires inpatient hospitalization or prolongation in existing hospitalization; in general, hospitalization signifies that the participant has been detained (usually involving at least an overnight stay) at the hospital or emergency ward for observation and/or treatment that would not have been appropriate in the physician's office or outpatient setting.

Complications that occur during hospitalization are AEs. If a complication prolongs hospitalization or fulfills any other serious criteria, the event is serious. When in doubt as to whether hospitalization occurred or was necessary, the AE should be considered serious. Hospitalization for elective treatment of a pre-existing condition that did not worsen from baseline is not considered an AE.

 Results in persistent or significant incapacity or substantial disruption of the ability to conduct normal life functions.

This definition is not intended to include experiences of relatively minor medical significance such as uncomplicated headache, nausea, vomiting, diarrhea, influenza, and accidental trauma (e.g., sprained ankle) which may interfere with or prevent everyday life functions but do not constitute a substantial disruption.

- Is a congenital anomaly or birth defect, or
- Is another important medical event (see below)

Important medical events that do not result in death, are not life-threatening or do not require hospitalization may be considered SAEs when, based on appropriate medical judgment, they may jeopardize the subject and may require medical or surgical intervention to prevent one of the outcomes listed above. Examples of such medical events include invasive or malignant cancers, intensive treatment in an emergency room or at home for allergic bronchospasm, blood dyscrasias or convulsions that do not result in hospitalization, or development of drug dependency or drug abuse.

A distinction should be drawn between serious and severe AEs. Severity is a measure of intensity whereas seriousness is defined by the criteria above. For example, a mild degree of

gastrointestinal bleeding requiring an overnight hospitalization for monitoring purposes would be considered an SAE, but is not necessarily severe. Similarly, an AE that is severe in intensity is not necessarily an SAE. For example, headache may be assessed as severe in intensity but would not be considered an SAE.

Medical and scientific judgment should be exercised in deciding if an AE is serious and if expedited reporting is appropriate.

## 6.4.1.4 Reporting of Serious Adverse Events

Prompt (within 24 hours) notification by the investigator to the Sponsor's designated Drug Safety and Pharmacovigilance vendor, i.e., MMS, of an SAE is essential so that legal obligations and ethical responsibilities towards the safety of participants and the safety of a study treatment under clinical investigation are met.

The Sponsor has a legal responsibility to notify both the local regulatory authority and other regulatory agencies about the safety of a study treatment under clinical investigation. The Sponsor will comply with country-specific regulatory requirements relating to safety reporting to the regulatory authority, institutional review boards (IRBs)/independent ethics committees (IECs), and investigators.

The investigator will review each SAE and evaluate the intensity and the causal relationship of the event to IMP/study procedure. All SAEs will be recorded from signing of informed consent until completion of the Safety Follow-up. SAEs occurring after the Safety Follow-up Visit and coming to the attention of the investigator must be reported only if there is (in the opinion of the investigator) reasonable causal relationship with the IMP.

The investigator is responsible for updating the EDC and providing notification to MMS Drug Safety and Pharmacovigilance of any SAE, whether deemed IMP-related or not, that a subject experiences during their participation in study within 24 hours of becoming aware of the event to:

MMS Drug Safety and Pharmacovigilance is responsible for providing notification to the Sponsor of any SAE as soon as they become aware of the event.

As a minimum requirement, the initial notification should provide the following information:

- Identifiable subject
- Identifiable event (including causality assessment)
- Identifiable IMP

#### • Identifiable reporter

MMS Drug Safety and Pharmacovigilance will request clarification of omitted or discrepant information from the initial notification. The Principal Investigator or an authorized designee is responsible for faxing or emailing the requested information to MMS Drug Safety and Pharmacovigilance within 24 hours of the request.

It is **not** acceptable for the investigator to send photocopies of the subject's medical records to the Sponsor in lieu of appropriate completion of an SAE Report Form. Additional information (copies of laboratory reports, consultant reports, copies of discharge summaries, etc.) should be provided on request to MMS Drug Safety and Pharmacovigilance. If an SAE Report Form is faxed or emailed, then the Principal Investigator must sign and date the form.

Initial notification via telephone does not replace the need for the investigator to complete and sign the SAE Report Form within the designated reporting time frames. Contacts for SAE reporting can be found on the protocol title page

All SAE reports submitted by the investigator will be reviewed by the study Sponsor and assessed for meeting criteria of suspected unexpected serious adverse reactions (SUSARs). All SUSARs will be reported by the Sponsor to competent national authorities and investigators according to local regulatory requirements and Sponsor policy.

An investigator who receives an individual case safety report describing a SUSAR or other specific safety information (e.g., summary or listing of SAEs) from the Sponsor will review and then file it along with the Investigator's Brochure and will notify the IRB/IEC, if appropriate according to local requirements.

#### 6.4.1.5 Follow-up of Adverse Events

All AEs experienced by a subject, irrespective of the suspected causality or seriousness, will be monitored until the event has resolved, until any abnormal laboratory values have returned to baseline or stabilized at a level acceptable to the investigator and Medical Monitor, until there is a satisfactory explanation for the changes observed or until the subject is lost to follow-up. If a subject is lost to follow-up and has not answered any phone calls from the site (at least 3 calls), a final proof of contact via certified letter is required (see Section 7.5).

The investigator is obligated to perform or arrange for the conduct of supplemental measurements and/or evaluations as medically indicated or as requested by the Sponsor and/or CRO to elucidate the nature and/or causality of the AE or SAE as fully as possible. This may include additional laboratory tests or investigations, histopathological examinations, or consultation with other health care professionals.

All AEs/SAEs that are still present after the last study drug administration (including AEs that have led to premature discontinuation), will be followed-up at the Safety follow-up visit. In case

the AE/SAE is still ongoing after that timepoint, this will be followed up until its resolution or until otherwise agreed between the Sponsor and the investigator.

Additional safety data collected after the Safety follow-up visit to follow-up the ongoing AE will not be included into the clinical database, if this was already locked; therefore the clinical database lock will not be delayed due to this situation. Any SAE will be followed up, if needed, after clinical database lock, and the information will be only stored in the safety database.

## 6.4.2 Pregnancy

Female subjects who become pregnant during the study will be withdrawn.

The investigator will attempt to collect pregnancy information on (i) any female participant or (ii) male participant's female partner (after obtaining the necessary signed informed consent) who becomes pregnant while participating in this study.

The investigator will record pregnancy information on the appropriate form and submit it to MMS Drug Safety and Pharmacovigilance within 24 hours of learning of the pregnancy. The pregnant participant /female partner will also be followed to determine the outcome of the pregnancy. Information on the status of the mother and child will be forwarded to the Sponsor. Generally, the follow-up will be no longer than 6 to 8 weeks following the estimated delivery date. Any termination of the pregnancy will be reported regardless of fetal status (presence or absence of anomalies) or indication for the procedure.

Abnormal pregnancy outcomes (eg, spontaneous abortion, fetal death, stillbirth, congenital anomalies, ectopic pregnancy) are considered SAEs.

# 6.4.3 Clinical Laboratory Assessments

The following laboratory variables will be determined as outlined in Table 4 below:

Table 4 Clinical Laboratory Assessments

Test	Parameters				
Hematology	CBC	Leukocytes (WBC)			
	Hb1Ac	Differential WBC			
	Hemoglobin	Platelets			
	Hematocrit				
	Erythrocytes (RBC)	Erythrocytes (RBC)			
Biochemistry	Sodium	GGT			
	Potassium	CPK			
	Magnesium	Total bilirubin			
	FSH (post-menopausal females only) a	Total protein			
	Calcium	Albumin			
	Chloride	Total Cholesterol			
	Glucose	Low-density lipoprotein			
	Creatinine	High-density lipoprotein			
	ALP	Triglycerides			
	AST	TSH, fT3 and fT4 a			
	ALT				

Coagulation	INR PT	aPTT
Serology	HBsAg a HCV a	HIV type 1 or type 2 a
Urinalysis	pH glucose ketones specific gravity HCG (females of child-bearing potential only)	nitrite protein bilirubin blood

AST = aminotransferase; ALP = alkaline phosphatase; ALT = alanine transaminase; CBC = complete blood count; CPK = creatine phosphokinase; FSH = follicle-stimulating hormone; GGT = gamma-glutamyl transferase; Hb1Ac = glycated hemoglobin; HBsAg = hepatitis B surface antigen; HCG = human chorionic gonadotropin; HIV = human immunodeficiency virus; INR = international normalized ratio; PT = prothrombin time; aPTT = activated partial thromboplastin time; RBC = red blood cells; fT3 = free tri-iodothyronine; fT4 = free thyroxine; TSH = thyroid-stimulating hormone; WBC = white blood cells.

Any value outside the normal range will be flagged for clinical interpretation by the investigator or designee at the site. In this study, ALT or AST > 2 times the upper limit of normal, or Child-Pugh class B and C (i.e., including total bilirubin, albumin, and INR values), will be exclusionary. For transaminase liver enzymes, a repeat laboratory assessment may be performed if outside of the normal range. If the transaminases remain elevated the investigator should consider stopping study medication and withdrawing the subject as described in Section 5.8.

A medical alert for potential Hy's laws cases (possible drug-induced liver injury) will be issued based on laboratory values and supported by Medical Monitor interpretation. Investigators, the Sponsor, Medical Monitor, and MMS (the Sponsor's designated vendor for Drug Safety and Pharmacovigilance) will immediately be notified when the above criteria have been met through a central laboratory alert. The AE eCRF should be completed within 3 business days. Every effort to determine the cause of the liver enzyme abnormalities must be made, and close monitoring should be initiated in conjunction with the Medical Monitor and in accordance with the FDA Guidance for Industry, Drug-Induced Liver Injury: Premarketing Clinical Evaluation, July 2009.

Criteria for potential Hy's law cases are as follows:

- ALT or AST  $\geq$  3 × ULN AND
- Total bilirubin  $\geq 2 \times ULN \text{ AND}$
- Alkaline phosphatase < 2 × ULN

Typically, all 3 analytes will be obtained from the same sample, but they may come from multiple samples taken within a 24-hour period. This requirement applies from the time the subject signs the ICF for the study until 4 weeks after the final protocol-defined study visit or the last known dose of study treatment (if the final visit does not occur).

<sup>a Measured only at Screening for eligibility; not included in subsequent safety labs.

Any clinically significant abnormalities from Screening labs must be discussed with the Medical Monitor to confirm eligibility of the subject. Additional testing during the study may be done if medically indicated. If a clinically significant abnormality is found in the samples taken after dosing, during the study, and/or at the safety follow-up visit, it should be recorded as an AE and the subject will be followed until the test(s) has (have) normalized or stabilized.

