### 1.3 Risk-Benefit Assessment

Whilst qEEG and ERP P300 results in humans are indicative of CNS penetration and target engagement, efficacy in subjects with PDD or DLB (in terms of cognitive, functional, or behavioral improvement) has not been established. Therefore, the benefits to study subjects of participating in this clinical trial are not yet known.

In clinical studies of ATH-1017, single SC administration of 2, 6, 20, 40, 60, and 90 mg in healthy young subjects, and multiple administration of 20, 40, 60, and 80 mg (SC, OD, over 9 consecutive days) in healthy elderly subjects, and 40 mg (SC, OD, over 9 consecutive days) in AD subjects were safe and well tolerated. Injection site reactions included pain, pruritus, and/or erythema, were mild in nature, and resolved without specific therapy. A potential risk for hepatotoxicity identified in nonclinical studies has not been observed in human studies but will be closely monitored in this study. To date, no CNS-specific adverse events have been observed in humans.

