Study drug will be administered by SC injection OD preferably during daytime; subjects must not take another dose within 8 hours of the preceding dose. The first SC injection of study drug will be performed on site under supervision. The subject should withhold study drug administration on the day of subsequent clinic visits; study drug administration will be done on site under supervision of site staff at these visits. Each subject is required to have a primary caregiver willing to accept responsibility for supervising or, if required, administering study drug, and assessing the condition of the subject throughout the study in accordance with all protocol requirements. During the double-blind treatment period, clinic visits will take place on Day 1 and thereafter at Weeks 2, 6, 12, 16, 20, and 26, with a safety follow-up visit scheduled 4 weeks after completion of the double-blind period at Week 30 (see Table 1 for Schedule of Assessments). On Day 1, after completion of the first dose, subjects will remain on-site for 2 hours for post-treatment clinical observation.

ADAS-Cog13, and assessments shall occur at clinic visits in the morning at approximately the same time they were performed during the initial baseline assessment (Visit 2b). Subjects will undergo post-baseline ERP P300 assessments at clinic visits (pre- and/or post-dose timepoints) as specified in Table 1.

Subjects may live at home, in a senior residential setting, or an institutional setting without the need for continuous nursing care, and should not be likely to experience a change in living conditions (e.g., institutionalization, moving to a different city, etc.), or change in primary caregiver, during participation in the trial period. The end of the study is defined as the date of the safety follow-up visit, Visit 9/Week 30. Subjects who terminate prior to Visit 8 are to complete the same assessments as Visit 8/early termination (ET).

Blood draws will take place at scheduled clinic visits for analysis of plasma concentrations of ATH-1017 (pro-drug) and ATH-1001 (active metabolite) (see Table 1 for Schedule of Assessments).

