# 5.8 Stopping Criteria

For all subjects, at any time during the study, study treatment should be discontinued and the subject will be withdrawn immediately if any of the following criteria/AEs are recorded:

- ALT or AST  $> 5 \times ULN$  for more than 2 weeks
- ALT or AST  $> 8 \times$  upper limit of normal (ULN)
- ALT or AST > 3 × ULN and total bilirubin > 2 × ULN, or international normalized ratio [INR] > 1.5
- ALT or AST  $> 3 \times$  ULN with symptoms (the appearance of fatigue, nausea, vomiting, right upper quadrant pain or tenderness, fever, rash, and/or eosinophilia > 5%)
- AEs:
  - Any SAE confirmed as probably or definitely related to the IMP
  - Any AE of severe intensity confirmed as probably or definitely related to the IMP and associated with clinically significant findings
     (Note: causality as determined by the Sponsor)

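### One of the four liver stopping limbs (ALT or AST > 5 × ULN for more than 2 weeks) cannot be judged when it falls due from the scheduled labs

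*Protocol*

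**What the plan says.** Protocol Section 5.8 lists four liver criteria, any one of which calls for stopping treatment and withdrawing the subject at once:

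- ALT or AST > 5 × ULN "for more than 2 weeks"
- ALT or AST > 8 × ULN
- "ALT or AST > 3 × ULN and total bilirubin > 2 × ULN, or international normalized ratio [INR] > 1.5"
- listed symptoms or eosinophilia alongside ALT or AST > 3 × ULN

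Section 7.4.2 repeats that meeting a Section 5.8 criterion obliges discontinuation.

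Section 3 fixes the visits: "clinic visits will take place on Day 1 and thereafter at Weeks 2, 6, 12, 16, 20, and 26". Table 1 marks safety labs at each of these and at the Week 30 follow-up, with none in between.

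On raised transaminases, Section 6.4.3 says: "For transaminase liver enzymes, a repeat laboratory assessment may be performed if outside of the normal range". It adds that if they stay raised "the investigator should consider stopping study medication and withdrawing the subject as described in Section 5.8". SAP Section 6.4.3 carries the same optional repeat and adds no interval.

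Section 1.3 says that a potential hepatotoxicity risk, found in nonclinical work, "has not been observed in human studies but will be closely monitored in this study".

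**The concern.** A criterion that depends on how long a value stays raised needs at least two measurements, the second close to the end of the stated period. Here the period is two weeks, the mandated measurements are four to six weeks apart, and the only sentence on repeating a transaminase test is permissive and undated.

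Section 5.8 handles its ECG criterion differently. A prolonged QTcF calls for at least two further ECGs within a short time, and the text says how to combine them. The liver duration limb has no such instruction, although it covers the one organ risk that Section 1.3 singles out.

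Safety is a primary objective. A site can follow the written plan exactly and still have a subject dosed daily beyond the two-week limit with nobody in a position to say whether the criterion has been met.

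**Working it through.** **Inputs.** Table 1 visit days are 1, 14, 42, 84, 112, 140, 182 and 210, with ±7 days at each visit after Day 1. The limb is > 5 × ULN for more than 14 days, so the earliest day it can be met is day 15 after onset. The plan gives no figure of its own to reproduce.

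**Step 1: spacing of scheduled labs after Week 2.** The nominal gap is the difference in visit days. The window range is that gap minus 14 to plus 14 days, since both ends can move by 7. Lateness is the nominal gap minus 15, for a subject first seen above 5 × ULN at the earlier visit and counting from that draw.

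| Interval | Nominal gap (days) | With windows (days) | Next draw after day 15 (days) |
|---|---|---|---|
| Weeks 2–6 | 42 − 14 = 28 | 14–42 | 13 |
| Weeks 6–12 | 84 − 42 = 42 | 28–56 | 27 |
| Weeks 12–16 | 112 − 84 = 28 | 14–42 | 13 |
| Weeks 16–20 | 140 − 112 = 28 | 14–42 | 13 |
| Weeks 20–26 | 182 − 140 = 42 | 28–56 | 27 |

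Weeks 26–30 (28 days) is the post-treatment follow-up. Relative to the 14-day limit, the gaps are 28/14 = 2, 42/14 = 3 and, at the window extreme, 56/14 = 4 times as long. A 28-day gap shortened fully at both ends is 14 days, which is still not more than two weeks.

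**Step 2: what scheduled draws would see.** Assume an elevation of length D days starts at a uniformly random time in a schedule with spacing g. Then P(at least one scheduled draw) = min(1, D/g), and P(two draws) = (D − g)/g, bounded between 0 and 1.

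| D (days) | One draw, g = 28 | Two draws, g = 28 | One draw, g = 42 | Two draws, g = 42 |
|---|---|---|---|---|
| 15 | 0.54 | 0 | 0.36 | 0 |
| 21 | 0.75 | 0 | 0.50 | 0 |
| 28 | 1.00 | 0 | 0.67 | 0 |
| 35 | 1.00 | 0.25 | 0.83 | 0 |
| 42 | 1.00 | 0.50 | 1.00 | 0 |

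On nominal dates, an elevation of 15 to 28 days is never seen twice. Two consecutive scheduled values above 5 × ULN would be consistent with the limb being met, but only 28 or 42 days after the first.

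**Step 3: who is left uncovered.** Take a subject above 5 and up to 8 × ULN with normal bilirubin and INR and none of the listed symptoms or eosinophilia. The > 8 × ULN limb, the bilirubin or INR limb and the symptom limb do not apply. The close monitoring in Section 6.4.3 belongs to the Hy's law alert, which needs bilirubin of at least 2 × ULN, so it does not apply either. Only the duration limb is left.

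**Step 4: pandemic provisions.** Section 7.2 lets Weeks 2, 6, 16 and 20 be done by tele-health, among other options. If no blood were drawn at those visits, the gaps would be 84 − 1 = 83 days and 182 − 84 = 98 days. This is conditional, because home visits and local laboratories are also listed.

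**The case against.** The strongest reply is that the protocol does provide follow-up outside Table 1:

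- Section 6.4.3 has out-of-range values flagged for clinical interpretation, and clinically significant abnormalities recorded as AEs and followed until they return to normal or settle.
- Section 6.4.1.5 obliges the investigator to arrange further tests where medically indicated or requested.
- Section 7.1.1 allows unscheduled visits with labs.
- Section 7 sends immediate safety concerns to the sponsor.
- Section 7.4.2 requires discontinuation for any safety finding that may endanger the subject and is at least possibly drug-related, whatever its duration.
- Section 4.4 provides weekly calls to the caregiver.

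Much of this stands. A competent site would probably repeat a value above 5 × ULN, so the delays above are what the written plan permits, not what one should expect to happen. But none of these routes sets a time, and a follow-up duty with no interval could be met by the next scheduled visit. An obligatory withdrawal criterion should not rest on that.

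A reader might also infer that Sections 5.8 and 6.4.3 flatly contradict each other, one obligatory and the other advisory. The text does not go that far. The advisory sentence follows one about any value outside the normal range, well below the Section 5.8 thresholds, and it refers back to Section 5.8. The two can coexist, but their relation is not stated.

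The SAP (Sections 6 and 8) records that the study stopped early. That limits what can still be changed in conduct. It does not alter what the text permitted, or the need to correct the wording before it is reused.

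**Conclusion.** The point holds for one limb of four. The criterion of ALT or AST > 5 × ULN for more than two weeks cannot be assessed on time from scheduled labs, and no passage requires a timed repeat. The nominal lateness is 13 or 27 days past the first day the limb could be met, with gaps of up to 56 days at the window extremes. These figures assume that no unscheduled sample is taken. The detection probabilities also assume a uniformly random onset and nominal visit dates.

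Three stronger readings are not supported:

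- That the liver stopping rule as a whole depends on duration. The other three limbs can be applied at any draw.
- That the duration limb can never be applied. An unscheduled repeat is allowed and would serve.
- That uneven repeat testing between sites distorts the liver comparison between arms. SAP Section 6.4.3 summarises liver tests by multiples of ULN, not by stopping rates. SAP Section 10.6.1 plans no comparison of AEs between groups. Nothing in the documents suggests that repeat practice would differ by blinded arm.

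This is a real gap in a safety rule and cheap to close, but it is not a failure of liver monitoring as a whole.

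**What to change.** Reconcile Protocol Sections 5.8 and 6.4.3 and Table 1 so that the protocol's own duration criterion can be assessed when it falls due. In the same edit, state how the advice in Section 6.4.3 to consider stopping relates to the withdrawal criteria in Section 5.8, and carry the agreed text into SAP Section 6.4.3. The trigger, the interval and the wording are for the sponsor's medical lead; no clinical rule is proposed here.

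The cost is protocol wording plus an occasional unscheduled blood draw in the few subjects with raised values, which Section 7.1.1 already permits. The downside is a small extra visit burden for those subjects.
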